10 DATA COLLECTION AND QUALITY ASSURANCE

10.1 Data Collection Forms

Information will be collected for each participant by the Study Coordinator, or a research assistant under their immediate supervision. For double-blinding, no member of the PI's research team that will interact with participants will know the stimulation codes that differentiate active vs. sham tDCS. The PI will generate this code list before the study is initiated, and then share it with the DSMB. The PI will not refer back to this code list until data collection is ended, and the PI will not administer study procedures to study participants. The research team will share de-identified data with the PI during the study, to troubleshoot or as needed, but no analysis of tDCS vs sham will be conducted until the end of the study.

Maintaining confidentiality of participant records will be achieved by storing these records in

-
-

password protected excel files on a lab computer, backed-up on the University's protected server, and also on external hard-drive in the lab by the Study Coordinator.

1. Qualtrics Survey - *Adverse events*
 - Contains information about any Adverse Events (both serious and non-serious). Data from this survey will be used to generate routine updates to the DSMB regarding adverse events. The survey is modeled off of the NIA templates for adverse event and serious adverse event logs.
2. REDCap DB - *AM/PM Randomization DB*
 - Enables participant assignment to the AM-session-first or PM-session-first condition, prior to the participant's baseline session.
3. REDCap DB - *Task Condition Randomization DB*
 - Enables participant assignment to one of 12 task varieties, during the participant's baseline session.
4. REDCap DB - *Participation DB*
 - Enables participant assignment to active or sham stimulation, and, if the participant is a younger adult, to either the dlPFC or parietal electrode placement. Will also contain information about each of the participant's visits.
5. Spreadsheet - *OA Contact Log*
 - Contains information about older adults who have been contacted about participating in the study.
6. Spreadsheet - *Screening Log*
 - Contains information about participant eligibility based off the Inclusion/Exclusion Criteria Screening Survey.
7. Paper log - *Payment Log*
 - Contains the subject's name and a place to sign to indicate payment was received.
8. Spreadsheet - *Blinding Key*
 - Links a Soterix stimulation code to either the active or sham condition. The study personnel will not have access to this file until the close of the study. [name] will maintain the key, and use it to setup the randomization scheme in the REDCap databases mentioned above.

○
○

10.2 Data Management

- All **Administrative Logs** in the form of spreadsheets will be maintained in a secure Google Drive folder on UChicago's GSuite, which will be periodically backed up to the Study Coordinator's computer. *Note:* this excludes the *Blinding Key* which only [name] and [name] will have access to.
- Study forms in paper/pencil format (see **Description of Evaluations**) will be kept in a locked file cabinet in the [name] Memory Lab.
- Electronic data from online surveys (see **Description of Evaluations**) will be maintained on the Study Coordinator's Lab Computer for backup, which will be automatically backed-up on the University server. It will be shared with the research team and the DSMB upon request.
- Electronic cognitive task data (raw and organized in Excel), blinded to tDCS condition (active, sham), will be maintained on the Study Coordinator's Lab Computer, which will be automatically backed-up on the University server. Additionally it will be uploaded to a private Open Science Framework project. It will be shared with the research team and the DSMB upon request.

10.3 Quality Assurance

10.3.1 Training

The Study Coordinator will be trained in study procedures by the PI, and in tDCS procedures by the PI's current research team, who have conducted tDCS research in the lab.

10.3.2 Quality Control Committee

The DSMB will review certain blinded data at the midpoint, as described elsewhere, and at other times they might request.

10.3.3 Metrics

Quality control metrics for outcome measures will be finding the expected effects of age-group (younger > older) on episodic memory (recollection) accuracy and working memory accuracy.

Moreover, for each participant, we expect hits to be greater than false alarms on these tasks. These and other aspects of quality and compliance (study forms, actigraphy) will be monitored by the Study Coordinator and PI.

-
-

10.3.4 Protocol Deviations

Protocol deviations will be reported to the PI by the Study Coordinator, and they will be documented by the Study Coordinator in the notes section of the Participation REDCap DB and made available for review by the DSMB.

10.3.5 Monitoring

The Study Coordinator, the PI, and the research team will work together to implement the data collection and monitoring procedures described here. They will conduct a pre-review of all appropriate materials prior to each DSMB meeting.

11 PARTICIPANT RIGHTS AND CONFIDENTIALITY

11.1 Institutional Review Board (IRB) Review

This protocol and the informed consent documents and any subsequent modifications will be reviewed and approved by the IRB or ethics committee responsible for oversight of the study.

11.2 Informed Consent Forms

A signed consent form (younger or older adult versions) will be obtained from each participant. All participants must be able to consent for themselves. The consent form will describe the purpose of the study, the procedures to be followed, and the risks and benefits of participation. A copy will be given to each participant and this fact will be documented in the participant's record.

11.3 Participant Confidentiality

No medical records will be accessed or created as part of this study, and as such, no HIPAA regulated data will be collected in this study.

Any data, specimens, forms, reports, and other records that leave the site will be identified only by a Participant ID to maintain confidentiality. All paper records will be kept in a locked file cabinet. Information will not be released without written permission of the participant, except as necessary for monitoring by IRB, the FDA, the NIA, and the OHRP.

11.4 Study Discontinuation

The study may be discontinued at any time by the IRB, the NIA, the OHRP, the FDA, or other government agencies as part of their duties to ensure that research participants are protected.

-
-

12 ETHICAL CONSIDERATIONS

The guiding ethical principles being followed by the study are those required by The University of Chicago SSD IRB as well as those provided by the NIA.

13 COMMITTEES

The Data Safety and Monitoring Board will be responsible for the following:

- Review the research protocol, informed consent documents and plans for data safety and monitoring as defined in this document;
- Recommend subject recruitment be initiated after receipt of a satisfactory protocol;
- Evaluate the progress of the trial, including periodic assessments of data quality and timeliness, recruitment, accrual and retention, participant risk versus benefit, performance of the trial sites, and other factors that can affect study outcome;
- Review study performance, make recommendations and assist in the resolution of problems reported by the Principal Investigator;
- Report to NIA on the safety and progress of the trial;

14 PUBLICATION OF RESEARCH FINDINGS

Any presentation, abstract, or manuscript will be made available for review by the sponsor and the NIA prior to submission.

○
○

## Analysis Plan

### PRIMARY ANALYSES

Set 1 (1a, 1b, 1c). The first set of primary analyses will estimate the effect of tDCS to left dlPFC on cognitive performance and the extent to which different aspects of the cognitive task will be impacted. These analyses will be done separately for episodic and working memory.

1.a This analysis will be done on younger adults only. We shall use a linear mixed (i.e., random participant-level intercepts) model with memory performance (defined as memory accuracy computed by subtracting false alarms from target hits) as the dependent variable and stimulation condition (stimulation vs. sham), session Time of Day (AM, PM), and task manipulations (stimulus format and difficulty) as within-subjects predictors along with session order as a covariate (session 1, session 2). Interaction terms between stimulation condition and both task manipulation and time of day will be used to examine the impact of these variables on the stimulation effect.

1.b This analysis will use the same model as in 1a (above), but including data from both younger and older adults and a corresponding age-group factor in the model. Interaction terms between age group, stimulation condition, and time-of-day will be used to determine whether the overall stimulation effect is the same for older as for younger adults, and if not, whether the difference varies by time of day.

1.c This analysis will assess the impact of preferred time of day on tDCS effects, using wrist-worn (minimum 7-days, max 12-days) accelerometry to measure preferred time of day (i.e. “Owl” vs “Lark”), and validation using the subjective Morningness-Eveningness Questionnaire (MEQ). For this analysis, accelerometry-derived variables capturing preferred time of days (eg, including wake time, rise time and midpoint of sleep) will be added as covariates to the model in 1.b., and interactions between these, time of day and stimulation effects will be evaluated.

Set 2. The second set of primary analyses will focus on dlPFC vs parietal vs sham effects in younger adults only. For these analyses, similar models to those described above will be used (e.g., 1a, 1c, 2), except we will include 3 levels for tDCS (dlPFC, parietal, sham). We will test the relative fit of three models: (1) a model in which parietal has the same effect as sham, (2) a model in which parietal has the same effect as dlPFC, and (3) a model in which the effect of parietal differs from the other two conditions.

All analyses will initially be performed without using the baseline performance measures. We shall then repeat each analysis adjusting for the baseline value of the cognitive measure being analyzed. To the extent that the cognitive measures are highly correlated across timepoints, the latter analyses will provide additional power.

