BSTIM Protocol – Version 4 (December 13, 2023)

Originally proposed DSMB protocol, with statistical analysis plan moved to Statistical Analysis File.

Effect of Noninvasive Electrical Brain Stimulation on Memory Performance at Different Times of Day in Younger and Older Adults

Study Principal Investigator:

[name], Professor, Department of
Psychology University of Chicago

Supported by:

The National Institute on Aging

1R21AG060444 : BRAIN STIMULATION AND TIME OF DAY IN COGNITIVE AGING

Study Intervention Provided by:

not applicable

Sponsor of IND (IDE):

not applicable

-
-

BSTIM:

Effect of Noninvasive Electrical Brain Stimulation on Memory Performance at Different Times of Day in Younger and Older Adults

Objectives

We have recently found that tDCS has a larger impact on episodic memory in the morning, but given the mixed literature on tDCS, we aim here to (1) complete a reliable replication attempt of these published tDCS findings, (2) extend this time-of-day tDCS research in new directions, including aging, and (3) explore interesting, yet secondary, aging and memory questions within our non-tDCS (baseline data) data.

Aim 1: Determine the extent to which tDCS to left dorsolateral prefrontal cortex (or dlPFC) boosts recollection accuracy and working memory performance as a function of time-of-day in younger and older adults.

Secondary: Assess the relationship between objectively measured sleep patterns and self-reported morning-evening preferences on memory performance, and possible interactions with tDCS.

Aim 2: Determine the extent that tDCS to dlPFC boosts information-specific processes compared to information-general cognitive control processes in younger and older adults. The cognitive tasks will experimentally pit information-specific (words, pictures) and cognitive control (easy, hard) to test dlPFC tDCS effects in each age group.

Secondary: Determine the regional specificity of tDCS on task performance in younger adults, by comparing the impact of tDCS to left dlPFC and left parietal cortex (an active stimulation control site, as in Gray et al., 2015).

Aim 3: Determine the extent to which a pre-post between-subjects tDCS design can improve the detection of stimulation effects, while also preserving the validity of the sham condition.

Design and Outcomes

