Power analysis: Our power analysis was based on our most recent and largest tDCS experiment with younger adults (Wong et al., in press, $n = 30$ per each between-subjects condition), which yielded a 12% difference in word test accuracy between sham (.23, $SD = .21$) and active tDCS (.35, $SD = .21$) in the 9 AM group, predicting that we would need 50 participants in each stimulation group in order to obtain a similar effect size (Cohen's $d = .57$, or a medium effect size) with 80% power at $p < .05$ (2 tailed, calculated with G-Power, v. 3.1.9.3). We therefore plan to test 50 younger adults and 50 older adults in each stimulation condition in order to detect effects of this magnitude. These sample sizes are considerably larger than most (if not all) of the between-subjects tDCS experiments on episodic memory published as of 2017. A sample size of 50 per condition also should yield sufficient power to detect the 2x2 interaction between brain stimulation (between-subjects) and time-of-day (within-subjects) in each age group, if we assume a similar effect size (partial eta squared = .06) for the interaction between time-of-day and stimulation we had obtained in younger adults in Wong et al. (in press), and also a .25 correlation between the repeated measures during AM and PM (80% power, alpha = .05).

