### STATISTICAL SIGNIFICANCE

A two-sided p-value cutoff of 0.05 will be used for all null-hypothesis significance testing. In addition, point estimates for all first order and interaction effects will be reported, together with 95% confidence intervals. Between-individual contrasts (e.g., overall treatment effects) will be standardized (i.e., equivalent to Cohen’s d). Results of all analyses performed will be reported (not just those that meet the 0.05 cutoff). Since Hypotheses 1-4 are distinct, we shall not make any adjustment for multiple testing across the corresponding analyses. Within each analysis, we shall use a hierarchical approach in which we

begin with an overall test of the null hypothesis at the coarsest level, separately for episodic and working memory, and only if that is statistically significant will we conduct further testing among subgroups.

Although the primary analyses will utilize the frequentist approach to estimating and testing, we will complement this with a secondary Bayesian analysis using the same model. For parameters capturing treatment effects or between-group differences in treatment effects (i.e., interaction terms), we shall use a weakly informative prior (e.g.,  $\text{Normal}(0, 1-10)$ ). The primary value of this analysis will be to provide more interpretable (i.e., probability) statements about the magnitude of the effects of tDCS and about the amount of information contained in the data.

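### The AM word-test contrast that sets 50 per arm is not a pre-specified test in the available SAP text, and as the testing rule reads it follows an overall test the arms were not sized for

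*SAP*

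**What the plan says.** Objective (1) in the protocol is to "complete a reliable replication attempt of these published tDCS findings". The finding is worded there as follows: "We have recently found that tDCS has a larger impact on episodic memory in the morning".

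The power analysis (Protocol, Sample Size and Randomization) is where the finding is given as numbers: "12% difference in word test accuracy between sham (.23, $SD = .21$) and active tDCS (.35, $SD = .21$) in the 9 AM group". It derives 50 per stimulation group from that difference, "with 80% power at $p < .05$ (2 tailed, calculated with G-Power, v. 3.1.9.3"). The same paragraph also claims 80% power for the 2x2 stimulation by time-of-day interaction, assuming a partial eta squared of .06 and an AM-PM correlation of .25.

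SAP Set 1 begins: "The first set of primary analyses will estimate the effect of tDCS to left dlPFC on cognitive performance". The same sentence goes on to ask which aspects of the task are affected. Analysis 1.a covers younger adults, separately for episodic and working memory. Its predictors are stimulation, time of day, stimulus format and difficulty, with session order as a covariate. It names interactions of stimulation with the task manipulations and with time of day.

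Under Statistical Significance the SAP promises that "point estimates for all first order and interaction effects will be reported, together with 95% confidence intervals". It also sets a hierarchical rule: within each analysis, an overall test comes first, and subgroup testing follows only if that test is significant.

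**The concern.** The stated 80% power belongs to one cell of the design: left dlPFC against sham, younger adults, AM session, word test. That contrast is neither a first-order effect nor an interaction, so the SAP's commitment to estimates and intervals does not clearly cover it. No analysis in the available text names it, and none says which result will count as replication.

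The hierarchical rule adds to this. If the cell contrast counts as subgroup testing, it can be tested only after a significant overall stimulation effect, averaged over sessions and formats. The investigators expect a larger effect in the morning, and averaging dilutes such an effect. At stake is whether the trial has its advertised power for the replication, and whether the choice of replication result stays open until the codes are broken.

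**Working it through.** **Inputs.** From the power analysis: difference .12, SD .21, two-sided .05, 50 per group, AM-PM correlation .25. Assumed, because the documents do not give them: SD .21 for each of the four format-by-session scores (averaged over difficulty), .25 for every cross-session correlation, and a word-picture correlation within session, r, of .25 to .75. The overall test is taken to be the stimulation effect averaged over the four scores.

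**1. The plan's own figure.** d = .12/.21 = .571. The normal approximation gives n = 2 × (1.960 + 0.842)² × (.21/.12)² = 48.1, so 49 per group. The exact t calculation gives 50 per group, with power 80.6% (d = .57) to 80.8% (d = .571). The stated 50 reproduces.

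**2. Power of the overall test.** The SD of the mean of four scores is .21 × √((6 + 4r)/16), which is .139 at r = .25, .148 at r = .50 and .158 at r = .75. Two-sample t, 98 df:

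| Where the .12 effect lies | Averaged effect | d (r = .25 to .75) | Power of overall test |
|---|---|---|---|
| AM words only | .12/4 = .03 | .22 to .19 | 19% to 16% |
| AM, both formats | .24/4 = .06 | .43 to .38 | 57% to 47% |
| All four cells | .48/4 = .12 | .86 to .76 | 99% to 97% |

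**3. Power to pass the overall test and then the AM-word contrast.** Simulation with 20,000 trials per case gives 18% to 15% for AM words only, 54% to 46% for AM in both formats, and about 80% for all four cells. Tested directly, the contrast has about 81% in every row.

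**4. The interaction that 1.a does name.** The SD of the AM-minus-PM difference, averaged over formats, is .21 × √(.5 + r). If the effect is in the AM for both formats, the interaction effect is .12, d = .66 to .51, and power is 90% to 72%. If it is in AM words only, the interaction effect is .06, d = .33 to .26, and power is 37% to 24%.

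**5. Estimating the AM-word effect from 1.a.** If the model holds only two-way stimulation terms and the truth is AM words only, the implied AM-word effect is the average effect plus half of each two-way difference: .03 + .06/2 + .06/2 = .09, against a true .12. With a stimulation by time by format term, or with an effect present in the AM for both formats, this shortfall disappears.

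**The case against.** A reader might infer that replication is never answered. The documents do not support that. The objective speaks of a larger morning effect on episodic memory and does not mention words. Analysis 1.a tests stimulation by time of day in younger adults for episodic memory, and the SAP promises an estimate and interval for that term. The power paragraph also claims power for it, so the word-test contrast is not the only sizing target.

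A reader might also infer that Set 1 simply pools words with pictures. It does not: format is a predictor with its own stimulation interaction. Averaging over format affects the overall test and, if no higher-order term is fitted, the time-of-day term. Nor do the documents say whether the earlier study had a picture test or what it showed, so an AM-words-only effect is an extreme case and not an established one. The .09 estimate needs that case and a strictly two-way model as well, and 1.a's wording does not exclude a three-way term.

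Finally, the SAP refers to Hypotheses 1-4, which are not in the available text; a replication hypothesis may be stated there.

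All of this stands, and it narrows the point. It does not supply a named replication test in the text available, or free the sizing contrast from the overall test. If the interaction is meant to be the replication test, the SAP should say so.

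**Conclusion.** The concern holds as a gap in pre-specification with a real cost in power. The AM word-test contrast behind the stated 80% is not named, and under the hierarchical rule it would be reached and passed about 15% to 18% of the time if the effect is confined to AM words, or 46% to 54% if it is a morning effect in both formats. If the effect is the same in all four cells, almost nothing is lost. The loss therefore depends on the effect being time-specific, which is what the investigators expect.

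These figures rest on the assumed common SD and correlations, on reading the overall test as an averaged stimulation effect, and on reading the cell contrast as subgroup testing. The sample size is adequate for the contrast itself. The time-of-day side of the replication is covered by the 1.a interaction.

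**What to change.** In SAP 1.a, name one replication contrast: younger adults, left dlPFC against sham, AM-session word-test episodic accuracy, two-sided .05, with its 95% interval reported beside the earlier .12. Exempt it from the overall-test rule; without the exemption, naming it does not restore the 81%. Estimate it from AM word scores directly, or from a model that includes stimulation by time of day by format.

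Report the stimulation by time-of-day interaction alongside it as the test of the larger morning effect. State that the overall Set 1 effect does not decide replication. Make the change before the stimulation codes are broken.

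The cost is SAP wording and one more pre-specified test at .05. It needs no added participants or data.

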6.2 Description of Evaluations

Cognitive Tasks:

Episodic Memory Task. We will cross stimulus type (words vs. pictures) with a recollection difficulty manipulation (items studied once or twice), all within-subjects. For the picture study list, participants will study words followed by a corresponding picture of the object (half colored pictures, half line drawings). Participants will decide if each picture is high or low detail, thereby drawing attention to perceptual features. For the word study list, participants will see the names of common objects and will be prompted to make one of two semantic judgments (Made in a factory? Found in house?), thereby drawing attention to conceptual features. We will give two recollection tests alternating across mini-blocks to avoid order effects. On the picture test blocks, verbal labels for the studied pictures will be intermixed with non-studied items, and participants will make one of three response options (studied as color, line, or new) followed by a confidence judgment. The structure of the word test blocks will be similar, whereby participants will make one of three response options (studied with a factory judgment, a house judgment, or new) in addition to the confidence judgment. Within each test, the items studied in the two different picture formats (or semantic judgments) will be matched on familiarity, so that participants will need to use recollection to make source judgments. Although pictures are typically better recollected than words, we have found that discriminating between these two different picture formats (namely, color or line judgments during the picture test) and these two different semantic judgments (namely, factory or house judgments during the word test) can be matched on difficulty with the repetition manipulation (i.e., comparing once-presented pictures to repeated words, Sarfan et al., 2014), allowing us to disentangle material-specific effects from recollection difficulty. Our primary dependent variable (DV) will be source recollection accuracy (the proportion of studied items attributed to the correct source, minus the proportion of non-studied items incorrectly attributed to that source). During each experimental session, subjects will perform the episodic memory task followed by the working memory task (described below).

-
-

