Working Memory Task. Similar to the episodic memory task, the working memory task will involve a stimulus manipulation (verbal vs. visuospatial working memory) as well as a difficulty manipulation, all manipulated within-subjects and across mini-blocks to control for order effects. Specifically, we will use the N-back task with a verbal version (i.e., presenting the numbers 1-9 in a varied sequence) and a matched visuospatial version (i.e., presenting a colored square in one of 9 locations on a 3x3 grid in a varied sequence). Based on neuroimaging work, both tasks rely on bilateral PFC regions, but the former relies more heavily on left PFC, and the latter more heavily on the right PFC (for meta-analysis, see Owen et al., 2005). Difficulty will be manipulated by varying the N in the N-back task into “easy” and “difficult” versions for both younger and older adults (1 and 2 back for older adults, 2 and 3 back for younger adults). Our primary DV will be proportion of targets correctly identified minus the proportion of lures incorrectly endorsed.

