6.2.2 Enrollment, Baseline, and/or Randomization

Enrollment & Randomization

Enrollment begins when the participant signs the informed consent form for the 3-session experiment, at the start of the first lab session (i.e., baseline/orientation day).

-
-

After successful screening, participants will be randomized to either the AM-session-first condition or to the PM-session-first condition using the AM/PM Randomization REDCap database. Just prior to the baseline session, the participant will be assigned to a cognitive task condition using the Task Condition Randomization REDCap database. Finally, just before the first tDCS session, the participant will be assigned to a Soterix stimulation code, and to an electrode placement (either PFC or parietal), using the Participation REDCap database.

Baseline Assessments

During baseline assessment participants will complete cognitive tasks, demographic information, and other forms (Table 6.1).

[Morningness-Eveningness Questionnaire](#) (MEQ) *online survey* - Participants will take the MEQ, assessing AM and PM testing preferences, which is correlated with physiological measures of circadian rhythms and predicts time-of-day effects on cognitive tasks in younger and older adults (Horne & Ostberg, 1976; see May & Hasher, 2017). Younger adults are expected to express at least a mild preference for PM testing (approximately 70% of younger adults in our prior sample), and older adults at least a mild preference for AM testing (typically 75% of older adults, see Yoon et al., 1999). (See Appendix).

[Actigraphy and Sleep Diary](#) *online survey* - During the initial orientation session participants will be equipped with an actigraphy watch and instructions for this and the sleep diary, and these data will be collected over a minimum 7-day period. During this period, participants will return to the lab for 2 testing sessions (AM/PM, nonconsecutively), returning the actigraphy watch and sleep diary on the final testing session. These measures will be used to help interpret the differential time of day effects (AM vs PM) on cognitive functions that we predict in younger and older adults, as well as the predicted interaction with tDCS brain stimulation.

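### The random-intercept-only model in SAP 1.a tests all three stimulation interactions against one pooled residual, so their standard errors can be wrong in either direction

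*SAP*

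**What the plan says.** SAP, Primary analyses, 1.a, states the model in full: "We shall use a linear mixed (i.e., random participant-level intercepts) model with memory performance". The bracketed definition leaves a participant intercept as the only random effect. Time of day (AM, PM) enters as a predictor, as do "task manipulations (stimulus format and difficulty) as within-subjects predictors", with session order as a covariate. Stimulation is interacted with time of day and with the task manipulations. Episodic and working memory are modelled separately. Analysis 1.b reuses the model with age group added, 1.c adds accelerometry covariates to 1.b, and Set 2 uses similar models. The SAP names no random slope, participant-by-session effect, other covariance structure or robust standard error.

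Protocol 6.2 shows that the factors are crossed. For episodic memory: "We will cross stimulus type (words vs. pictures) with a recollection difficulty manipulation (items studied once or twice), all within-subjects". For working memory there is "a stimulus manipulation (verbal vs. visuospatial working memory) as well as a difficulty manipulation", also within-subjects.

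The SAP's Statistical significance section says that "point estimates for all first order and interaction effects will be reported, together with 95% confidence intervals".

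**The concern.** Stimulation by time of day is the replication question of Aim 1. Stimulation by format and by difficulty are the questions of Aim 2. An intercept-only model assumes that participants differ in overall level but not in their AM-PM, format or difficulty effects. If they do differ in those effects, one shared residual cannot serve all three tests: one interaction may be rejected too often while another is tested too cautiously, and a reader of the results cannot tell which.

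The plan itself gives reasons to doubt the assumption.

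- **Time of day, both tasks.** Protocol 6.2.2 says that morning-evening preference "predicts time-of-day effects on cognitive tasks in younger and older adults" and expects at least a mild PM preference in "approximately 70% of younger adults in our prior sample". AM-PM effects should therefore differ between people, yet 1.a and 1.b contain no preference term. AM and PM sessions also fall on different days, so any day-level fluctuation becomes participant-by-time variance.
- **Episodic task.** Source accuracy is a hit proportion "minus the proportion of non-studied items incorrectly attributed to that source". Non-studied items have no once or twice level, so the once and twice scores of one test in one session appear to share a false-alarm rate. This is an inference from the scoring rule; the protocol does not state it.

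**Working it through.** **The plan's own figure.** Protocol section 9, Power analysis: means .23 and .35, SD .21, so d = .12/.21 = .57. At 50 per group, two-sided .05, the noncentral t gives power of about 0.81, so the stated n reproduces and is not in dispute. For the interaction the protocol assumes two repeated measures, AM and PM, with correlation .25. With only two scores per person a random intercept is the whole within-person structure. The SAP model has eight.

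**Inputs.** 2 × 2 × 2 = 8 scores per person per task, hence 7 within-person contrasts. Protocol 5.4 restricts primary analyses to completers, so the data are taken as balanced. There are 50 per arm and no true interaction. All variances below are assumptions.

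**Notation.** e = residual variance; v, f, d = participant-by-session, -format and -difficulty variance; w = level-specific session-by-format variance (such as a shared false-alarm rate); h = sum-to-zero participant × time × format variance.

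**True contrast variances.** Time of day 4v + 2w + e; format 4f + 2w + e; difficulty 4d + e.

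**Variance the SAP model uses for all three.** e + [4(v + f + d) + 6w + 8h]/7.

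**Actual type I error.** 2(1 − Φ(1.96/√R)), where R = true variance / pooled variance.

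| Assumed setting | Time of day | Format | Difficulty |
|---|---|---|---|
| 1. No participant-by-condition variance | 5.0% | 5.0% | 5.0% |
| 2. v = .15, e = .60 | 13.8% | 3.6% | 3.6% |
| 3. v = f = d = .10, e = .65 | 8.3% | 8.3% | 8.3% |
| 4. v = .10, f = d = .30, e = .65 | 5.0% | 14.0% | 14.0% |
| 5. v = .10, f = d = .60, e = .65 | 2.4% | 18.5% | 18.5% |
| 6. w = .10, e = .65 | 6.8% | 6.8% | 3.7% |
| 7. h = 0.1 / 0.25 / 0.5, e = 1 | 3.9 / 2.6 / 1.4% | same | same |

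Row 2 in full: true 4(.15) + .60 = 1.20; pooled .60 + .60/7 = .686; R = 1.75; 1.96/√1.75 = 1.48; 13.8%.

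Row 7 at h = 0.5: true 1; pooled 1 + 4/7 = 1.571; R = .636; 1.4%.

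**How far the .25 constrains this.** It depends on the reading.
- As a correlation between single cells, with no slope variance, v = r − .25 and e = 1 − r, where r is the within-session correlation. At r = .30/.40/.50 the time-of-day test has 7.8/13.8/19.9%.
- As a correlation between four-cell session means, the cross-session cell correlation is (1 + 3r)/16. An intercept-only structure then needs r = 1/13 = .077. At r = .20/.30/.50 the test has 9.8/14.1/23.2%.

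**Preference mix alone.** A 70/30 split with an assumed gap of 1.0 cell SD in the AM-PM effect gives variance .70 × .30 × 1² = .21 = 2v, so v = .105. With e = .75 − .105 = .645, R = 1.065/.705 = 1.51, and time of day has 11.1%.

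**When at least one error is understated.** With h = 0, the three true variances average e + (4/3)(v + f + d + w). The pooled value is e + (4/7)(v + f + d) + (6/7)w, which is smaller unless every component is zero. The largest of the three then exceeds the pooled value. With h > 0 this can fail: v = 0.1, h = 0.4, e = 1 gives 4.2% for time of day and 1.6% for the other two. The general condition is that the largest of the three exceeds the mean of all seven.

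**Simulation check.** With the session-order covariate and 5,000 runs per setting, row 2 gave 14.0/3.7/3.8%, row 5 gave 2.8/18.5/18.1% and row 6 gave 7.1/6.4/3.9%. Participant-level difference scores gave 4.5–5.7% throughout. In separate 8,000-run simulations, which included h = 0.5, contrast scores gave 4.7–5.4%. These runs check the algebra; they say nothing about which variances are true.

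**The case against.** **No size or direction comes from the documents.** This stands. Every variance above is assumed, the .25 has two readings, and the preference gap and false-alarm share are illustrative. The time-of-day test can be anti-conservative, correct or conservative.

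**A reader might infer that at least one of the three tests must be anti-conservative.** The documents do not support that. It follows only if participant heterogeneity lies in time of day, format, difficulty or level-specific combinations of them. If it lies mainly in sum-to-zero higher-order interactions, all three standard errors can be too large (row 7).

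**The plan partly covers it elsewhere.** Analysis 1.c models time-of-day preference with its interactions, but it is a separate analysis. It does not change the errors in 1.a or 1.b, and it leaves day-level fluctuation untouched. The SAP also repeats each analysis adjusted for baseline, which may absorb some format or difficulty heterogeneity. That does not alter the initial analyses, and a single baseline session at a variable time cannot supply a person's AM-PM difference.

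**The hierarchical gate limits false claims.** The SAP does not define its overall test. If that is the overall stimulation test and stimulation has no effect, the 13.8% of row 2 falls to .05 × 13.8% = 0.7%. If stimulation has a real overall effect, the gate tends to open and gives less protection. It never corrects the confidence intervals, which are reported regardless.

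**Reach.** No error rate was computed for the three-way age test in 1.b, for 1.c or for Set 2. Overall between-participant contrasts in Set 2 are unaffected; the point applies to its interaction tests.

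**Conclusion.** The point holds in its conditional form. The error term stated in SAP 1.a is correct for a given interaction only if that contrast's variance equals the average over seven contrasts. Nothing in the documents supports that equality, and Protocol 6.2.2 together with testing on separate days makes zero participant-by-time variance unlikely. Illustrative type I error runs from about 1.4% to 20% or more, assuming balanced data, equal residual variance across cells and the variances listed. Which interaction is affected, in which direction and by how much cannot be determined from the documents. The overall stimulation effect is tested against between-participant variation and is not affected. This should be fixed before the codes are broken, because the choice of error term bears directly on the Aim 1 and Aim 2 interactions.

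**What to change.** In SAP 1.a, carried into 1.b, 1.c and the interaction tests of Set 2, test each stimulation interaction against its own participant-level error, in one of two ways:

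- **Contrast scores.** Compute one score per participant (AM minus PM, adjusted for session order; format difference; difficulty difference) and compare arms on it.
- **Fuller mixed model.** Add participant-by-session, participant-by-format and participant-by-difficulty random effects, with Satterthwaite or Kenward-Roger degrees of freedom. For the episodic task, add participant-by-session-by-format if once and twice scores share a false-alarm rate. Name the contrast-score test as the fallback for non-convergence.

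Only the contrast-score route was simulated; the fuller model's error rate was not. The cost is SAP wording and a small change to the model code. The downsides are wider intervals for interactions whose error is now understated and some convergence risk with the fuller model.

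An editorial correction, with no effect on the fit: 1.a lists stimulation among the within-participant predictors, whereas Protocol 9.1 makes it a between-participant factor.
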